### Schema

**Population:** 43 Patients with liver-dominant or liver-only metastatic disease from any primary histology **or** patients with primary hepatocellular or biliary cancer.  
ECOG performance status of 0, 1 or 2

**Registration Visit**  
Decision made to undergo radioembolization  
Informed Consent  
Verify baseline laboratory and imaging studies  
(contrast enhanced CT or MRI of the liver)

**Pre-treatment evaluation:**  
Staging arteriogram in preparation for radioembolization (coil embolization as necessary)  
Injection of Tc-99m labeled macroaggregated albumin (MAA) SPECT & Planar imaging of Liver, 3 Phase Liver CT Simulation, SPECT scan of Tc-99m MAA

**Day of treatment Visit 1(Day 0):**  
Radioembolization as per pre-planned prescription  
Post-treatment PET-CT to determine dose from radioembolization

**Day after treatment Visit 2(Day 1)**  
Post-treatment PET-CT to assess potential migration of spheres from implantation  
(subset of patients)

**Follow Up**  
Symptom guided physical exam, Serum Chemistry, CBC with Differential and Platelets, ECOG Performance Status, Adverse Event Assessment and Tumor Imaging.  
Follow-up visits will be scheduled at 1 week, 1 month, 3 months, and then every 3 months for one year, every 6 months for 1 year and then annually for 3 years or death whichever comes first.

## **1.0 Introduction**

### **1.1 Abstract**

This protocol for human research study is conducted according to US and international standards of Good Clinical Practice (International Conference on Harmonization (ICH) Guidelines) and applicable government regulations (e.g. Title 45, Part 46 Code of Federal Regulations).

The development of radioembolization with microspheres represents a significant advance in the treatment of patients with metastatic disease to the liver. [1,2] This technique uses semi-empirical formulas for dose calculation that rely on body surface area or crude volumes as the determinants of dose. Moreover, dose is assumed to be uniformly distributed throughout the treated volume. Although the efficacy of treatment and limited side effects are evidence of high intratumoral doses with minimal radiation to normal liver, there have been few attempts to quantify the actual doses delivered. Knowledge of these doses may allow more accurate determination of the effect of dose on response, improved algorithms for prescription of the safest and most effective dose for each patient, and safer integration of additional treatment to the area with either microspheres or external beam radiation. Therefore, we are proposing a new technique to better characterize the dose deposition of radioactive microspheres. The research plan will be based on the recent publication of positron emission from Yttrium 90 (Y-90), which can be utilized to image sphere distribution on a positron emission tomography (PET) scanner, without the administration of additional radiolabeled tracer. Three dimensional dose distributions will be generated and fused onto the CT data of patients to display doses to tumors and normal tissues.

### **1.2 Background**

The current methodology for determining the prescribed dose for patients to be treated with radiolabeled microspheres likely leads to suboptimal treatment of hepatic malignancies, with most patients being either overtreated or undertreated. The development of a novel technique for defining actual dose delivered will better define the activity required to achieve specific doses, and begin to support the transition from a model of dose prescription based primarily on body surface area to one that predicts the dose to both tumor and normal tissues.

The current formulae for determining the prescribed activity to patients to be treated with radiolabeled microspheres are crude and do not take into account significant variations in tumor size, shape, or location. There are two radiolabeled microsphere products currently available for treating patients with liver tumors (metastatic or primary): SIR-Spheres (Sirtex Medical, North Sydney, Australia) and Therasphere (Nordion, Ottawa, Canada). The formula most commonly used for SIR-Spheres is largely driven by body surface area:

$$A \text{ [GBq]} = \text{BSA} - 0.2 + (\text{TV}/\text{TLV})$$

where A = activity, GBq = Gigabecquerels (units), BSA = body surface area, TV = tumor volume, and TLV = total liver volume. This may be multiplied by the lobe factor (fraction of the total liver volume being treated) for patients in whom whole liver treatment is not being pursued. The formula used for calculation of activity in Therasphere administration is:

$$A \text{ [GBq]} = (\text{D [Gy]} \times \text{m [kg]})/49.38$$

where D is the desired dose in Gy, m is the tumor mass in kg. Dose is set to a nominal 100-120 Gy, based on an expected uniform distribution of microspheres over the treated region. However, there is no data available to date that would definitely confirm this. Moreover, this should not be expected to be true. This is due to the existence of hypervascular malignancy with blood supply derived from the hepatic arterial system and normal tissue deriving its blood supply from the portal vein—all within the treated volume.

Neither one of these formulas, nor any others in routine use, takes into account the differences in expected dose based upon the size, shape, and location of tumors. In fact, the prescription is simply the total activity to be administered, without any calculation of the dose to be delivered from this activity. Additionally, there is almost no calculation of expected normal tissue doses, with the exception of the use of Tc-99m macro-aggregated albumin (MAA) in order to quantify the lung shunt at the time of angiography prior to treatment. These limitations in the current prescription methodology hamper the ability to move this treatment technique forward, because without doses to both normal tissues and tumors it is not possible to ascribe better responses or increased side effects to the doses received. Therefore, in the ten years since this treatment has become available, there has been little or minimal advancement in the treatment technique.

The emission of positrons from Y-90 has recently been used to generate positron emission tomographs of radiolabeled microsphere distribution [3]. A similar technique has been used to measure the absorbed dose in an anatomical phantom – a laboratory stand-in for a patient – after treatment with SIR-spheres [4]. However, to our knowledge this technique has not been routinely performed in patients.

With the availability of a new technique to quantify the dose to tumors and normal tissues, it will be possible to correlate response and toxicity with actual dose delivered. A second potential application will be the correlation of the activity on the MAA scan with the actual dose deposition. It will be valuable to determine whether the MAA scan is a reliable predictor of dose distribution. With this relationship better defined, we may be able to escalate the dose delivered in many patients in order to improve the control rates and decrease doses in patients who are expected to have higher doses to normal tissues.

### **1.2.1 Preliminary Data**

The 3D dose absorbed in a patient is calculated by convolving the activity distribution  $A(x, y, z)$  with the dose kernel for Y-90 source, according to the following expression.

$$D(x, y, z) = \frac{1}{\lambda} \iiint K(x - x', y - y', z - z') A(x', y', z') dx' dy' dz',$$

where  $\lambda$  is the decay constant of Y-90 isotope and  $K$  is the dose kernel. The activity distribution in the equation above is due to electrons emitted by the source, but the measured PET scan data is the activity distribution due to emitted positrons. As a result, one can rewrite the above equation in the following form,

$$D(x, y, z) = \frac{1}{\lambda \gamma} \iiint K(x - x', y - y', z - z') A^p(x', y', z') dx' dy' dz',$$

where  $A^p$  is the measured activity due to positrons and  $\gamma$  is the conversion factor. Since the PET scanner's resolution is not sufficient to resolve individual spheres, the dose kernel is calculated for a volume element of the size equal to that of the PET scanner's voxel size, which is 0.4 x 0.4 x 0.3 cm. The whole volume of the voxel is assumed to be filled with tissue, with uniformly distributed electron sources in it that emit electrons with energy spectrum corresponding to that of beta electrons of Y-90 [5]. The Fluka Monte Carlo code was used to calculate the voxel dose kernel (VDK) in tissue. All pertinent interactions were turned on during the simulations and up to  $10^9$  histories were simulated to reduce the uncertainties.

Care has to be taken in order to properly process the measured activity  $A^p$  (activity due to positrons). Current Siemens PET/CT scanners do not provide an option for specifying imaging-related parameters for Y-90 isotope. Therefore Y-86 template was used in our image acquisition procedure, which has its own tracer parameters that are different from those of Y-90. However, the Y-86 template can be used during image acquisition as long as one experimentally determines the calibration factor  $\gamma$  for Y-90 microspheres using the same PET scanner that is used for the subsequent in-patient dose reconstruction (one must use the same imaging template for determining the calibration factor as well as for patient scanning). It is interesting to note that in this case the herein defined calibration factor  $\gamma$  is the ratio between the branching ratios of Y-90 and Y-86.

The calibration factor  $\gamma$  for the Siemens Biograph 16 slice PET/CT scanner available at our center was determined by injecting 740 MBq of  $^{90}\text{Y}$ -chloride into a 1 L water bag. Subsequently, the "hot" water bag was scanned together with a "cold" identical size water bag using the PET scanner (to account for the scanner's noise). After the scan, the activity in the "cold" water bag was subtracted from the activity value of the bag containing  $^{90}\text{Y}$ -chloride. The corrected measured activity was divided by the known total activity at the time of scanning to determine the calibration factor (an average value for the calibration factor was obtained out of seven measurements) that will be used in dose calculations of every patient treated with microspheres.

Figures 1 and 2 show the calculated isodose distribution as well as the dose volume histogram of one of the patients recently treated by Y-90 microspheres.

[figure not shown]

Fig. 1: Reconstructed in-patient dose distribution superimposed on patient's axial CT data. The red, green and blue contours designate the tumor, liver and right kidney, respectively.

[figure not shown]

Fig 2: Dose volume histogram for tumor, liver, right kidney and gallbladder. The numbers indicate the percent line of the maximum dose, 134.7 Gy.

## 2.0 Objectives

### 2.1 Primary Objective

- To determine the relationship between radiation dose to 70% of the tumor volume as determined by post-treatment PET-CT and local control at 6 months.

### 2.2 Secondary Objectives

- To evaluate the ability of PET-CT to reproducibly determine dose to tumor, normal liver, and other surrounding organs
- To determine the stability of microsphere location by examining the changes in dose in a subset of patients with PET-CT scans performed on Day 0 and Day 1
- To determine the relationship of dose predicted by Tc-99m labeled Macro-aggregated albumin (MAA) imaged using SPECT versus post-treatment dosimetry
- To determine the effect of dose delivered on local control and normal tissue complications
- To measure the perfusion of the tumor for correlation with dose deposition, based on arterial phase CT measurements
- To evaluate overall survival for 5 years after Visit 1, Day 0.

### **3.0 Study Plan**

This study will be a single arm registry study to evaluate the dose received by ability of PET-CT to determine dose delivered via radioembolization to the liver for metastatic disease. Patients will be staged and treated in the standard fashion, but will undergo a number of imaging studies in order to better analyze the dose of radiotherapy delivered. These imaging studies include a Tc-99m MAA SPECT scan (carrying no additional radiation exposure) as well as 1-2 PET-CT scans (a limited radiation exposure is necessary with each scan).

This is a prospective single-arm registry study being performed in order to validate a novel method of determining dose deposition from radioembolization by performing post-treatment PET-CT scan. Forty three patients will be enrolled over an expected recruitment time of 1.5 to 2 years. We will utilize these data to investigate the relationship between dose delivered to targets and local control. A subset of patients will undergo a second PET-CT with contrast CT on Day 0, and another subset of patient will have a second PET-CT on Day 1. All other procedures will be consistent with the standard of care. Details of the PET-CT procedure can be found in Appendix II.

### **4.0 Patient Selection Inclusion & Exclusion**

#### **4.1 Inclusion Criteria**

- 4.1.1 Patients must be at least 18 years of age.
- 4.1.2 Patients must have liver-dominant or liver-only metastatic disease from any primary histology. Patients with primary hepatocellular or biliary cancer are also eligible.
- 4.1.3 Patients must be clinical candidates for radioembolization with either SIR-spheres or Therasphere due to metastatic or primary malignancies of the liver.
- 4.1.4 Women of child bearing potential must have a negative serum pregnancy test no more than 72 hours prior to registration.
- 4.1.5 ECOG performance status (PS) of 0, 1 or 2.
- 4.1.6 Ability to understand and willingness to sign a written informed consent and HIPAA authorization for release of medical information.
- 4.1.7 Complete Blood Count (CBC), Chemistry Panel (CMP) and Coagulation Panel (PT, & INR) no greater than 4 weeks prior to registration.
- 4.1.8 Diagnostic imaging of the abdomen utilizing either CT with contrast, MRI, or PET/CT no greater than 6 weeks prior to registration.

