## **4.5 Patient Registration Procedure**

Patients will be consented at the time when the decision to pursue radioembolization is made. No protocol-specific workup will take place prior to obtaining informed

consent. However, at this time it will be determined that the patient has had a complete staging workup within the last 4 weeks including:

- Diagnostic imaging of the abdomen utilizing either CT with contrast, MRI, or PET/CT
- Complete metabolic panel (CMP)
- Complete blood count (CBC)
- Coagulation studies (PT, INR)

Eligible patients will be entered on study centrally by the Fox Chase Cancer Center QA Coordinator or their designee. Following registration, participants must begin protocol related treatments and evaluations within 14 days of registration. If a participant does not receive protocol therapy following registration, the participant will be recorded as withdrawn from study and will be replaced. The QA Coordinator must be notified of cancellations and withdraws as soon as possible.

Participants may be registered from 9:00 am to 5:00 pm excluding holidays and weekends by calling the QA Coordinator at [contact]. The site's investigator or designee will then fax the completed registration form, entire, complete and signed informed consent document and HIPAA authorization documents and the completed eligibility checklist to [contact]. The QA Coordinator or designee will notify the site's investigator or their designee by email when participant registration is confirmed and the sequence number has been assigned. Participants must be registered and have received a sequence number assigned by the QA Coordinator prior to the initiation of treatment.

Exceptions to the current registration policies will not be permitted.

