## **5.0 Study Procedures**

### **Pretreatment Visit**

A 3 Phase Liver CT simulation must be performed before Visit 1, Day 0 (The treatment Initiation Day). This simulation may occur before or after the staging angiogram, coil embolization, Tc-99m MAA injection, and planar and SPECT imaging of the participant's liver.

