### **Visit 1 (Day 0)**

Visit 1 will take place after the pretreatment visits, and will be referred to as Day 0, the day of radioembolization. Visit 1 will include the following procedures:

- Radioembolization as per standard clinical protocol
- PET-CT performed just after the radioembolization in order to measure Yttrium-90 activity for in-patient dose reconstruction
- Subset of patients will get contrast CT

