### **Follow-up Visits**

Participants will be followed for 5 years or until death, whichever comes first. Follow-up visits will be scheduled at 1 week, 1 month, 3 months, and then every 3 months for one year, every 6 months for 1 year and then annually for 3 years or death whichever comes first

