## 6.0 Study Calendar

	Registration Visit	Pre treatment Visit(s)	Visit 1 / Day 0	Visit 2/ Day 1	Follow up
Informed consent & HIPAA A	X				
Medical history	X				
Symptom Guided Physical exam G	X				X
ECOG Performance Status	X				X
CBC w/diff, plts B	X				X
Serum chemistry B	X				X
EKG (as indicated)	X				
β-HCG	X E				
Coagulation Studies B	X	X			
3 Phase Liver CT Simulation		X			
Staging Angiogram		X			
Coil Embolization		X			
Tc-99m (approx 5mCi) MAA Injection		X			
Planar and SPECT Imaging of Liver		X			
Adverse Event Assessment			X	X	X H
PET-CT C,D			X	X	
Tumor Imaging F	X				X I

A: Must be completed less than 28 days prior to registration and prior to any protocol specific tests or procedures.  B: CBC and CMP will be drawn at each follow-up visit, Coagulation studies include PT and INR. Coagulation studies must be performed for eligibility however results will not exclude patient participation.  C: Visit 1, Day 0 post treatment PET CT and contrast CT for subset of participants, Day 1 PET CT.  D: 24 hours +/- 3 hours after Day 0  E: See Section 4.4 for more information – Must be negative within 72 hours of first treatment related procedure or scan  F: Repeat imaging is encouraged to be the same modality (PET-CT, MRI, or contrast CT) as that in baseline study.  G: Physical exam with investigator where he/she reviews symptoms with the participant and addresses any issues that are identified by the participant. This is not the same as a complete physical exam, intentionally.  H: Record only AE's possibly, probably, or definitely related to the visit 2 / day 1 PET/CT scan. Possibly, probably or definitely related AE's must be followed until resolution or 30 days after visit 2.  I: Follow up tumor imaging begins with the month 3 follow up visit.
					

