## 8.0 Statistical Considerations

In this study, we will evaluate the dosages received by tumors and surrounding tissue using PET-CT data. The primary objective is to determine the relationship between radiation dose to 70% of the tumor volume and local control at 6 months. We will conduct this analysis at the tumor level, as different tumors may receive different doses of radiation, and may have different progression statuses at 6 months. We will use standard summary measures such as means, medians, ranges, and standard deviations to characterize the dosages received by tumor and other tissue. We will use percentages and frequency tables to evaluate other characteristics such as tumor histology, number of liver tumors per patient, and volume of liver tumors.

We will determine the relationship between radiation dose and local control at 6 months using regression models with Generalized Estimating Equations (GEE) to account for within-patient correlation. We will use logistic regression to adjust for potentially confounding factors such as tumor volume, primary histology, and SIR-Spheres versus Therasphere intervention. We will also determine the relationship between radiation dose to healthy tissue, and side effects such as fatigue, nausea, pain and elevated liver function tests. Each

side effect will be characterized as present or absent, and we will test the relationship between radiation dose to the relevant type of healthy tissue and each side effect. For example, we will look at the relationship between dose to the normal liver and elevation of liver function tests.

In further secondary analyses, we will explore the relationship between the distribution of activity measured by PET-CT, and the distribution predicted by T-99m labeled MAA. This can be translated into predicted dose. We will calculate differences between PET-CT and MAA doses, and present the data graphically. We will use the method proposed by Bland & Altman (2007) to assess the agreement between the two methods. Finally, in a subset of patients, we will explore the change in dose measured by PET-CT scan between day 0 and day 1. The dose at day 1 will be adjusted to account for the decay of the yttrium-90 using  $A=A_0e^{-(0.693t/T_{1/2})}$ . Observed changes in dose may be due to microsphere migration, and our main interest is to look for a systematic change in dose received based on this migration.

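### The last protocol liver tests can be 42 days old or more on Day 0, and the liver-toxicity analysis defines no baseline, so elevation that precedes treatment can be scored as a side effect

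*Combined protocol and SAP*

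**What the plan says.** Five parts of the protocol bear on this point.

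- **Age of the screening panel.** Section 4.1.7 requires "Complete Blood Count (CBC), Chemistry Panel (CMP) and Coagulation Panel (PT, & INR) no greater than 4 weeks prior to registration". Section 4.5 repeats the 4-week limit for the metabolic panel.
- **Registration to start.** Section 4.5: "participants must begin protocol related treatments and evaluations within 14 days of registration".
- **Start to treatment.** Section 5.0: "Visit 1 will take place after the pretreatment visits, and will be referred to as Day 0, the day of radioembolization". The CT simulation also has only to precede Day 0. Neither statement gives a longest interval.
- **When chemistry is drawn.** The Section 6.0 calendar marks blood count and serum chemistry at registration and follow-up. Coagulation is marked at registration and at the pre-treatment visits. No laboratory test is marked on Day 0 or Day 1. Footnote B adds "CBC and CMP will be drawn at each follow-up visit, Coagulation studies include PT and INR". The first follow-up is at one week: "Follow-up visits will be scheduled at 1 week, 1 month, 3 months, and then every 3 months for one year".
- **How the results are used.** Normal tissue complications are a secondary objective (Section 2.2). Section 8.0 scores each side effect as present or absent and gives the liver as its example: "we will look at the relationship between dose to the normal liver and elevation of liver function tests". It states no baseline value, no change rule and no adjustment for a pre-treatment value.

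**The concern.** The chemistry panel is outcome data in this study. It supplies the liver-test endpoint that is set against normal-liver dose, so the pre-treatment value matters for the analysis as well as for entry.

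The patients have liver-dominant or liver-only metastases, or primary hepatocellular or biliary cancer, and Sections 4.1 and 4.2 set no liver-test limits. Elevation before treatment is therefore plausible. Without a baseline in the endpoint, two kinds of elevation would be scored as side effects although treatment did not cause them:

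1. elevation already present on the registration panel;
2. elevation that arose between that panel and Day 0.

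The registration panel could deal with the first kind if Section 8.0 used it. Nothing the protocol schedules can deal with the second.

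Adverse-event forms do not fill the gap, because Section 7.0 records only events attributed to the PET/CT scans. Liver toxicity from radioembolization will be visible mainly through the protocol panels. What is at stake is misclassification of the endpoint, and with it a blurred dose-toxicity relationship.

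**Working it through.** The plan states no maximum age for liver tests on Day 0, so there is no figure of its own to reproduce. The age follows from the permitted windows.

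**Inputs**

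- Panel to registration: at most 4 weeks = 28 days (Section 4.1.7).
- Registration to start of protocol treatments and evaluations: at most 14 days (Section 4.5).
- First pre-treatment evaluation to Day 0: *g* days, not limited in Section 5.0. The values of *g* below are assumptions.
- Day 0 to first follow-up panel: 7 days (Section 5.0, Follow-up Visits).

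**Formulas**

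Maximum age on Day 0 = 28 + 14 + *g*. Maximum age at the 1-week visit = 28 + 14 + *g* + 7.

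| *g* (assumed) | Age on Day 0 | Age at 1-week visit |
|---|---|---|
| 0 | 42 days (6 weeks) | 49 days |
| 7 | 49 days (7 weeks) | 56 days |
| 14 | 56 days (8 weeks) | 63 days |
| 28 | 70 days (10 weeks) | 77 days |

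**Two readings of the 14-day rule**

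- If radioembolization itself must begin within 14 days, *g* adds nothing and the maximum on Day 0 is exactly 42 days.
- If the first pre-treatment evaluation meets the rule, the maximum is 42 + *g*, with no stated ceiling. The wording covers evaluations as well as treatments and limits only their beginning, so this is the more natural reading.

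**From timing to endpoint**

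Take a patient whose liver tests are normal on the registration panel, become elevated through disease before Day 0, and remain elevated at one week. On a present-or-absent score with no baseline, that patient has the side effect. A patient elevated at registration and unchanged afterwards is scored the same way. A chemistry value shortly before Day 0, used as the reference, would reclassify both.

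No misclassification rate can be worked out. The documents give neither the distribution of these intervals nor the frequency of pre-treatment elevation.

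**The case against.** The strongest counter-case has five parts.

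- **The windows are maxima.** Reaching 42 days needs a panel drawn on the earliest permitted day and a start on the last permitted day. Nothing shows that many patients, or any, will get there. This stands: 42 days on Day 0 and 49 days at one week are limits under the windows, not typical values. A reader might infer that baselines will generally be more than six weeks old. The documents do not support that, and going beyond 42 days also depends on how the 14-day rule is read.
- **The analysis uses no baseline, so its age is beside the point.** This is half right. The missing baseline is the more basic gap, and the age of the panel matters once a baseline is defined. That is why the two need fixing together.
- **A fresher panel cannot separate disease from radiation.** A reader might infer that it would. It would not: the study has a single arm, and disease course after Day 0 stays mixed with treatment effect at every visit. Only the pre-treatment part is removed. Misclassification unrelated to dose would also act mainly as noise, and the documents do not show that pre-treatment worsening tracks normal-liver dose.
- **Standard care probably includes laboratory tests near treatment.** Section 3.0 leaves other procedures to standard of care, so such results may exist. The protocol neither requires nor collects them, and the point is limited to protocol data.
- **Second treatments are partly covered.** The 1-month visit, with its chemistry panel, may fall on the day of a second radioembolization. The gap mainly concerns the first treatment.

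A reader might also extend the point to blood counts and renal values. Section 8.0 names fatigue, nausea, pain and elevated liver function tests, and no haematological or renal endpoint. The documents give no analysis that those values would affect.

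**Conclusion.** The point holds as a modest improvement to a secondary analysis. Under the permitted windows the last protocol liver tests can be up to 42 days old on Day 0, and older if the first pre-treatment evaluation satisfies the 14-day rule. Because Section 8.0 scores elevation without a baseline, elevation that precedes treatment can be counted as a side effect.

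The 42-day figure assumes that both windows are used in full, and the larger values in the table rest on assumed intervals to Day 0. The consequence for the endpoint is an inference from the scoring rule; its size is unknown. The primary objective and the sample size are not affected.

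**What to change.** 1. **Study Calendar, Section 6.0.** Mark serum chemistry in the Pre treatment Visit(s) column, on the coagulation draw already scheduled there. If there are several pre-treatment visits, take it at the last one before Day 0. Placement matters: a sample from the start of a work-up with no stated time limit could itself be old by Day 0.
2. **Section 8.0.** Define the last chemistry value before Day 0 as the baseline for the liver-test endpoint. Score elevation as new or worsened relative to that value, or keep the present-or-absent score and adjust for the baseline value.

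The cost is one routine test per patient on an existing blood draw, so 43 tests for the planned 43 patients at one each, plus two short text edits. The age of the baseline then becomes the interval from the last pre-treatment visit to Day 0. The protocol still does not limit that interval, so the date of the sample should be recorded and its age on Day 0 reported. Eligibility, treatment and the primary analysis stay as they are.
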